**7) Risks to Subjects**

Bright light therapy has an excellent safety profile and has been shown to be well tolerated by most patients. Side effects are infrequent; the most common ones are mild headache,

	Protocol Name:	Management of post-TBI fatigue with light exposure
	Principal Investigator:	[name]., ABPP/Cn
	Primary Contact Name/Contact Info:	[name], [contact] , [name]
	Date Revised:	3/9/16
	Study Number:	IF1556212

eyestrain, nausea and agitation. Side effects generally remit spontaneously. Study exclusion criteria were chosen to maximize safety. Subjects entering the study are screened by the research coordinator using the Mini International Neuropsychiatric Interview (MINI) for any history of bipolar disorder or manic episodes. Those who endorse any past history of bipolar disorder or manic episodes are immediately disqualified from the study. Those who do qualify are contacted bi-weekly during the light therapy phase of the study to check in for any symptoms of mania, adverse events or other health concerns. Qualified subjects are also explicitly instructed to contact the PI and research team of any health problems they sustain while in the light treatment phase of the study. Other risks in the study are related to loss of private information and emotional discomfort or distress from personal questions asked during interviews and assessment screenings. These issues will be monitored for safety.

### 8) Provisions for Research Related Harm/Injury

We will ask subjects to inform us of any new or intensified symptoms or health problems that they experience while using the light box. If significant adverse effects are experienced, the participant will be directed to discontinue treatment temporarily and consult their physician. Subjects will be withdrawn from the study if they experience any clinically significant side effects beyond those anticipated or if side effects are severe. We will ask participants not to alter medication use during the study unless it is medically necessary, and to notify the research team if alterations are made.

It is possible that some of the questions asked during interviews may make the participant feel uncomfortable. However, answering these questions isn't mandated. Also, there always exists the potential for loss of private information; however, there are procedures in place to minimize this risk. These procedures include (but are not limited to) keeping paper documents in locked cabinets and using passwords to protect electronic files.

### 9) Potential Benefits to Subjects

Participants may experience improvements in fatigue, mood, or sleepiness. They may also experience no benefits. There is much discussion in the literature on the most effective wavelength for treating sleep and depression. DRL may still have an effect on mood and sleep but it is rarely significant. Thus, it is one of the traditionally used controls for BWL (31, 32). We expect benefits to occur in the bright white group only.

### 10) Provisions to Protect the Privacy Interests of Subjects

Participants' privacy interests will be protected by ensuring that all communication of sensitive or personal information is done in private conversations with project CRC's. CRC's are trained to

	Protocol Name:	Management of post-TBI fatigue with light exposure
	Principal Investigator:	[name]., ABPP/Cn
	Primary Contact Name/Contact Info:	[name], [contact] , [name]
	Date Revised:	3/9/16
	Study Number:	IF1556212

interview subjects respectfully and with sensitivity to privacy concerns, particularly when discussing potentially sensitive topics relating to personal function and behavior (e.g., regarding personal care or emotional distress). They are trained to listen attentively and empathically but without inappropriate familiarity. Participants are given the option of not responding to questions that they do not want to respond to. When attempting follow up with participants, telephone messages that maybe left do not identify the individual as a research subject and include no personal information about their medical condition.

### 11) Economic Impact on Subjects

It is not expected that participants will incur any costs by participating in the research.

### 12) Payments to Subjects

Subjects will be paid \$20 by check for completion of each study assessment (including \$10 for a screening assessment prior to T1). Upon completion of follow-up, interested participants will be offered a discount coupon to purchase their own light box if they wish to do so. In order to issue checks, the Mount Sinai Department of Finance may need to collect private health information from participants, such as social security number, for tax reporting purposes. If participants do not wish to disclose their social security number, they can waive their compensation during their first visit by telling the research staff that they do not wish to receive payment.

### 13) Consent Process

The consent process will take place in a private testing room at the BIRC.

Before the subject has signed the consent form, agreeing to participate in the study, the research coordinator will determine if the subject has capacity to provide informed consent. Verbal feedback will be solicited from potential subjects in order to judge their capacity to consent, according to the University Of California San Diego Brief Assessment Of Capacity to Consent (UBACC). They will be asked to state in their own words what the purpose of the study is, what they are expected to do, and what the risks and benefits are. If they fail to provide correct answers, they will receive the explanation of the study again. If they fail again to provide correct answers to any questions, they will not be accepted in the study. If necessary, a mental status examination will be administered. Subjects will be encouraged to contact the principal investigator if they have questions about the protocol.

	Protocol Name:	Management of post-TBI fatigue with light exposure
	Principal Investigator:	[name]., ABPP/Cn
	Primary Contact Name/Contact Info:	[name], [contact] , [name]
	Date Revised:	3/9/16
	Study Number:	IF1556212

If the patient is deemed capable of consenting, the consent process will proceed according to SOP HRP-090 Informed Consent Process for Research.

**14) Process to Document Consent in Writing**

Consent will be documented using the standard PPHS consent template.

**15) Vulnerable Populations**

Indicate specifically whether you will include or exclude each of the following populations:

Include	Exclude	Vulnerable Population Type
	x	Adults unable to consent
	x	Individuals who are not yet adults (e.g. infants, children, teenagers)
	x	Wards of the State (e.g. foster children)
	x	Pregnant women
	x	Prisoners

This research involves cognitively impaired adults. In order for the subject to participate in research, he/she must demonstrate the capacity to give informed consent by attaining a score of 20 on the UBACC, as described in “Consent Process” above. Subjects who do not attain a score of 20 will be excluded from the study.

**16) Multi-Site Human Research (Coordinating Center)**

Mount Sinai will be the coordinating and main research center. Data from all sites (Centre for Neuro Skills and Mount Sinai) will be stored on the same electronically encrypted databases initially created at Mount Sinai. Centre for Neuro Skills research staff will be given access to these databases to enter their research data.

**17) Community-Based Participatory Research**

N/A

**18) Sharing of Results with Subjects**

There are no plans to share data with subjects although data will be provided to research subjects or their providers on request.

	Protocol Name:	Management of post-TBI fatigue with light exposure
	Principal Investigator:	[name]., ABPP/Cn
	Primary Contact Name/Contact Info:	[name], [contact] , [name]
	Date Revised:	3/9/16
	Study Number:	IF1556212

**19) External IRB Review History**

N/A

**20) Control of Drugs, Biologics, or Devices**

Light boxes and actigraphs will be stored in locked cabinets in the Brain Injury Research Center.

	Protocol Name:	Management of post-TBI fatigue with light exposure
	Principal Investigator:	[name]., ABPP/Cn
	Primary Contact Name/Contact Info:	[name], [contact] , [name]
	Date Revised:	3/9/16
	Study Number:	IF1556212

## 6. Analyses and Statistical Plan

### a. Data Processing

We will follow all relevant federal regulations regarding confidentiality and data security in research. We will review forms for completeness and accuracy prior to data entry. The database for the project will be established in REDCap, a web-based data management system. REDCap minimizes data entry errors by using menu-driven modules designed to accept only the valid range of values for each variable. Double-entry will reduce the chance of other errors

[name] will carry out Actigraphy data analyses on a de-identified encrypted database. The Actiware 5 software calculates sleep/wake statistics based on night intervals marked by the scorer, i.e., it provides these statistics for each interval (night), as well as a mean of all intervals (nights). Once the night intervals are correctly marked, the software scores each epoch (minute) as sleep or wake, based on a specific internal algorithm and provides analysis of data, including sleep onset latency, sleep efficiency, sleep time, wake time, % sleep, % wake, naps, resting and normal night time sleep. The Actigraphy software does not provide circadian activity rhythms analysis. [name] will export edited epoch-by-epoch activity data to SAS programs to perform standard circadian activity analysis including calculation of Amplitude, Acrophase, Mesor, and the F-statistic. The activity level per epoch (minute) is used to estimate circadian activity rhythms. Circadian activity rhythms are analyzed by fitting each subject's activity data to a 5-parameter extended cosine model.

### b. Data Analyses: Overview

We will calculate descriptive statistics for all measures. We will examine distributions and address substantial non-normality using data transformations, as necessary. If we detect a significant baseline group imbalance on a demographic or clinical variable, we will include that variable as a covariate in subsequent analyses. Dropouts and treatment completers will be compared on baseline variables. We will examine associations among demographic characteristics and outcome measures to identify necessary covariates for subsequent analyses.

We will fit random effects models to test the primary hypotheses, examining the effects of treatment over time. This model is a preferable alternative to traditional repeated measures ANOVA or ANCOVA, in that it takes into account the correlated nature of repeated measurement within an individual. The model allows us to examine the influence of demographic and injury characteristics prior to the inclusion of the treatment effect. We will conduct analyses on the full Intent-To-Treat sample (all subjects randomized) using full maximum likelihood estimation. We will determine model fit using Akaike's Information Criteria.

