### c. Hypothesis Testing

*H1: Individuals receiving daily BWL treatment will report significant reductions in fatigue from baseline compared to those receiving DRL.* The primary outcome measure, GFI, will be the dependent variable in the multi-level regression. We will enter time into the model first and examine fit. We will add any demographic or study measures identified as potential confounders in the preliminary analyses, and examine improvement of fit. Finally, we will add the treatment effect to the model and examine differences in fit to determine the presence and strength of the treatment effect over time. The same analyses will be conducted using our secondary fatigue outcome measure, the TBI-QOL Fatigue.

	Protocol Name:	Management of post-TBI fatigue with light exposure
	Principal Investigator:	[name]., ABPP/Cn
	Primary Contact Name/Contact Info:	[name], [contact] , [name]
	Date Revised:	3/9/16
	Study Number:	IF1556212

*H2: Individuals receiving daily BWL treatment will report significant reductions in daytime sleepiness and depressed mood as well as improvements in sleep quality and circadian rhythms from baseline compared to those receiving DRL.* Testing of this hypothesis will be identical to that for H1, with ESS (sleepiness), Neuro-QOL Depression (mood), NeuroQol Sleep (sleep quality) and circadian rhythm measures (from Actigraphy) as the dependent variables.

*H3: Treatment effects will be maintained one month after treatment completion.* Pilot data suggests that the positive effects of BWL persist beyond termination of active treatment. To address whether treatment effects are indeed maintained one month after treatment completion, we will extend the multilevel analysis for H1 to include data from the T3 follow-up assessment. One advantage of a third assessment is that the possibility of time as a non-linear effect can be explored. Model fit for a linear versus non-linear time effect will be compared to determine best fit. As in H1, any demographic or study measures identified in the preliminary analyses will be added, with examination of improvement of fit. Finally, we will add the treatment effect to the model to examine the persistence of the treatment effect over time.

d. Research Questions

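### H1 model: T1 GFI is best used through a common baseline mean, with a very short covariate list fixed in advance instead of imbalance testing

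*Combined protocol and SAP*

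**What the plan says.** All references are to the part headed Analyses and Statistical Plan, unless stated otherwise.

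**Baseline GFI.** Section c (Hypothesis Testing) makes GFI the dependent variable of a multilevel regression. H1 states that the bright-light group "will report significant reductions in fatigue from baseline compared to those receiving DRL". Time enters first, then covariates, then treatment: "Finally, we will add the treatment effect to the model and examine differences in fit to determine the presence and strength". The text does not say whether treatment enters as a main effect, an interaction with time or both, nor whether the two arms share one T1 mean. Section e (Statistical Power) describes a treatment-by-time, pre-post design with 40 per arm. It gives 90% power for the treatment effect (effect size 0.37) and 81% for the interaction (0.32), without saying which of the two tests H1.

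**Covariates.** Section b (Data Analyses: Overview) has two rules that depend on the trial's data. The first is "If we detect a significant baseline group imbalance on a demographic or clinical variable, we will include that variable as a covariate". The second is "We will examine associations among demographic characteristics and outcome measures to identify necessary covariates for subsequent analyses". Section c carries the result into H1: "We will add any demographic or study measures identified as potential confounders in the preliminary analyses, and examine improvement of fit". Fit is judged by AIC ("We will determine model fit using Akaike's Information Criteria"). No covariate list is fixed for H1. Age, gender and injury severity are named in section d, but for the exploratory RQ3, where the list is left open.

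**Analysis set.** "We will conduct analyses on the full Intent-To-Treat sample (all subjects randomized) using full maximum likelihood estimation".

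**The concern.** Two points are at stake, one larger than the other.

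First, a model with a treatment main effect, a time effect and their interaction leaves the T1 means free in each arm. With complete T1 and T2 data, its interaction is the between-arm difference in mean change. Randomisation guarantees that the arms share one population mean at T1, and a change-score comparison does not use that fact. Constraining the T1 means to be equal, or adjusting T2 GFI for T1 GFI, uses the same data and generally gives a more precise estimate. If the plan means free T1 means, power on the primary outcome may be left unused.

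Second, a significance test of baseline balance is a poor way to choose covariates in a randomised trial. A significant difference is chance, and it does not show that the variable predicts GFI. The adjusted H1 model is therefore not known until the data are seen, and a variable may enter for a reason unrelated to its value for precision.

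**Working it through.** **1. The plan's own power figures.** Inputs from section e: N = 80, 5% level, effect sizes 0.37 and 0.32. I read these as Cohen's f (an assumption, supported by the match below). Noncentral F with 1 and 78 df, λ = N·f²:
- f = 0.37: λ = 80 × 0.1369 = 10.95, power 90.5% (plan 90%).
- f = 0.32: λ = 80 × 0.1024 = 8.19, power 80.7% (plan 81%).

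Both reproduce. I take f = 0.32 to be on the change scale, as a pre-post interaction implies.

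**2. Effect of a common T1 mean.** Let ρ be the T1–T2 correlation of GFI and k = SD(T1)/SD(T2). In units of the T2 variance, the error variance is 1 + k² − 2ρk for change scores and 1 − ρ² after T1 adjustment. The ratio is

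R = (1 − ρ²)/(1 + k² − 2ρk), and 1 − R = (k − ρ)²/(1 + k² − 2ρk).

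So R never exceeds 1, and equals 1 only when k = ρ. Power uses λ = 8.19/R with 1 and 77 df. For example, with k = 1 and ρ = 0.5, R = 0.75/1 = 0.75, λ = 10.92, power 90.4%. The documents give neither ρ nor k, so both are assumed over a range:

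| k | ρ 0.3 | ρ 0.5 | ρ 0.7 | ρ 0.8 | ρ 0.9 |
|---|---|---|---|---|---|
| 1.0 | 93.9% | 90.4% | 86.6% | 84.6% | 82.6% |
| 0.9 | 91.6% | 87.6% | 83.5% | 81.7% | 80.7% |
| 0.8 | 89.1% | 84.9% | 81.4% | 80.7% | 82.6% |

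The comparison value is 80.7%. Estimating the T1 slope inflates the variance by about 1 + 1/76. Where k = ρ this takes power from 80.7% to 80.2%, the worst case of about half a point.

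**3. How often the imbalance rule fires.** The plan names at least 12 baseline variables: age, gender, injury severity, GFI, TBI-QOL Fatigue, ESS, the Neuro-QOL Depression, Sleep and Anxiety scales, the CNS Vital Signs index, CFQ and SWLS. At an assumed 5% threshold (the plan says only that the imbalance is significant) and with independence, the chance of at least one flag is 1 − 0.95¹² = 46%. If the nine scales correlate 0.3, 0.5 or 0.7 (assumed), simulation gives 42, 38 or 32%.

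**4. What the rule does to the H1 estimate.**
- Free T1 means, complete data: adding a main-effect covariate changes the arm-by-time estimate by zero.
- Free T1 means, 15% of T2 missing, ρ = 0.5, one covariate correlating 0.3 or 0.4 with GFI: the shift has an SD of 0.063 or 0.086 standard errors (600 simulated trials).
- Common T1 mean, selected against fixed covariates (4,000 simulated trials): SD 0.18–0.19 standard errors if no covariate is prognostic.
- Type I error in that last simulation: 4.9% with the rule, 5.0% with a fixed list.

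**5. Cost of a fixed list.** Take five df: age 1, gender 1, severity 2 (three levels assumed), site 1 (two groups assumed). With q adjustment terms including T1 GFI, chance correlation with arm inflates the variance by about 1 + q/(80 − q − 3). That is 1 + 1/76 for T1 alone, and 1 + 6/71 (72 residual df) with the list. If none of the five is prognostic:

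| k, ρ | T1 only | T1 plus five df |
|---|---|---|
| 1.0, 0.3 | 93.6% | 92.0% |
| 1.0, 0.5 | 90.0% | 87.9% |
| 1.0, 0.9 | 82.1% | 79.4% |
| 0.9, 0.7 | 83.0% | 80.4% |
| 0.8, 0.8 | 80.2% | 77.4% |

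The cost is about 1.6 to 2.8 points. In simulation the list breaks even when it explains about 7–8% of the residual T2 variance.

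**The case against.** The strongest reply has four parts.

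The covariate rule hardly matters on the reading that best fits the plan. This stands: with free T1 means the shift is zero with complete data, and under a tenth of a standard error with 15% missing. Simulations with a common T1 mean do give larger shifts, 0.35–0.48 standard errors, with the 5% verdict changing in 3–7% of trials across the scenarios run. But the larger shifts need two covariates with residual correlation 0.3–0.4. If independent, these would explain 18–32% of the variance left after T1 GFI (2 × 0.09 to 2 × 0.16). The documents do not support that as a headline.

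The power gain may be small. This also stands. The protocol describes fatigue as stable after the first year, which suggests a higher ρ. Entry requires a minimum fatigue score, which may make k less than 1. Both point away from the 13-point end of the range.

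A covariate list can cost more than T1 adjustment gains. This stands too, and it limits the fix.

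The plan already has safeguards: analysis of all randomised participants, full maximum likelihood, and treatment entered last. A reader might infer that covariates are picked to favour the treatment result, or dropped on AIC. The text says neither: fit is examined, but no removal rule is given, and the choice precedes the treatment term. A reader might also infer an inflated error rate, because taking the smallest p-value among four permitted analyses would give 7.5–8.8% in simulation. Nothing in the plan says the sponsor would do that. The two rules followed as written keep the rate near 5%.

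What survives is that a better use of T1 GFI is available from data already collected, and that the imbalance test is not a sound basis for adjustment.

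**Conclusion.** The point holds as a cheap improvement. On the best-fitting reading (free T1 means), H1 has 80.7% power with 80 completers at f = 0.32. A common T1 mean would raise this to about 83–94% over ρ from 0.9 down to 0.3 with equal SDs. The gain falls to nothing, or a loss of about half a point, when k is close to ρ. If the sponsor already intended a common T1 mean, there is no gain and only the wording needs completing.

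The imbalance rule is the lesser matter. It would bring in at least one variable in about 32–46% of trials by chance, with little effect on the estimate under free means. It deserves more attention once a common T1 mean is adopted, because covariates then do move the estimate.

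A reader might conclude that the 81% is wrong or that the primary test is invalid. Neither follows: the 81% reproduces, and no type I error inflation was found. The result rests on reading the effect sizes as Cohen's f on the change scale, and on assumed values of ρ, k and the 5% imbalance threshold.

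**What to change.** Amend sections b and c for H1 as follows.

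1. Name one contrast: the between-arm difference in GFI at T2, tested at the 5% level.
2. Estimate it by the likelihood model with T1 and T2 GFI as responses and a common T1 mean in both arms. This keeps every randomised participant, as section b intends.
3. Use T2 GFI regressed on arm and T1 GFI as a sensitivity analysis. It should not be primary, because it drops participants without T2 and 15% attrition is planned.
4. Drop the baseline-imbalance test and the outcome-association screen as covariate rules for H1. Fix in advance a very short list of covariates expected to be prognostic, chosen from age, gender, injury severity and site. State their coding, let their coefficients differ by time so that they adjust the T2 response, and make no selection by fit.
5. Keep T3 for the maintenance hypothesis (H3 in section c, H2 under Objectives).

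The cost is SAP wording; no new data are needed. The downside is in item 4: a list using five df costs about 1.6 to 2.8 points of power if none of it is prognostic. Where the T1 gain is small, that could leave power at about 77–80%, below the present 80.7%. The common T1 mean is therefore the core of the change, and the list should hold only covariates expected to explain residual variance.

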*RQ1: We will assess whether treatment with BWL is associated with changes in circadian rhythms and improvements in anxiety, cognition and life satisfaction using the analyses described for H1, with Neuro-QOL Anxiety, CNS Vital Signs Neurocognitive Index and CFQ (cognition), and SWLS (life satisfaction) as the respective dependent variables.*

*RQ2: As it is not clear whether BWL's effects on PTBIF are direct effects or secondary to changes in other domains, we will examine whether PTBIF scores are mediated or moderated by mood, sleepiness, sleep quality and circadian rhythms. These analyses will focus on the magnitude of the effect, as recommended by Kraemer et al. We will use a fixed-effects approach in which the dependent variable is the GFI pre-post change. We will compare the between treatment group effect sizes for those with and without the respective potential mediator or moderator. An effect will be considered present if a substantial difference in effect size is observed. Results from these exploratory analyses could be used to guide the design of future RCTs that would focus on those subjects most likely to respond to BWL.*

*RQ3: Because current research suggests that age, gender and injury severity may be associated with treatment outcome, we will examine these individual characteristics and any others that the literature suggests may be relevant at the time of analysis. We will add these variables to the multilevel model one at a time and test to determine if the variable improves fit. Continuous variables that improve the fit will be examined further by determining the correlation between them and GFI separately for the two treatment groups, and comparing the strength of the correlations.*

e. Statistical Power

[The sample size for this study will provide adequate power to test the primary hypothesis. We will recruit enough subjects to fill the Treatment (DRL-BWL)-by-Time (pre-post) repeated measures design (40 subjects per treatment group, total N = 80). This design achieves 90% power to test the treatment effect using a Geisser-Greenhouse Corrected F Test with a 5% significance level, based on an effect size of 0.37, and achieves 81% power to test the Treatment-by-Time interaction using a Geisser-Greenhouse

	Protocol Name:	Management of post-TBI fatigue with light exposure
	Principal Investigator:	[name]., ABPP/Cn

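### Full maximum likelihood is the only estimator named; it slightly understates the variance behind the final treatment estimate, and a REML refit of the final model would correct this at almost no cost

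*Combined protocol and SAP*

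**What the plan says.** Section 6.b (Data Analyses: Overview) sets the model class, "We will fit random effects models to test the primary hypotheses", and one estimator for the whole randomized sample: "We will conduct analyses on the full Intent-To-Treat sample (all subjects randomized) using full maximum likelihood estimation". It adds the fit criterion: "We will determine model fit using Akaike's Information Criteria". No REML fit, degrees-of-freedom method or small-sample correction appears anywhere in 6.b to 6.e.

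Section 6.c (Hypothesis Testing) applies this to H1: "The primary outcome measure, GFI, will be the dependent variable in the multi-level regression". Time is entered first, then any confounders found in preliminary analyses, and last "we will add the treatment effect to the model and examine differences in fit". That final step is meant to show both whether there is a treatment effect and how large it is. The same procedure is carried over to TBI-QOL Fatigue, to the sleepiness, mood, sleep and circadian outcomes, to the three-visit model, and (in 6.d) to anxiety, cognition and life satisfaction.

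Section 6.e (Statistical Power) quotes 90% power for the treatment effect and 81% for the treatment-by-time interaction with 40 per arm, in each case "using a Geisser-Greenhouse Corrected F Test with a 5% significance level". This is the only place in section 6 where a significance level is given.

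**The concern.** ML estimates a variance by dividing the residual sum of squares by the number of independent units, with no allowance for the fixed effects fitted. An F test divides by the error degrees of freedom. The model in 6.b to 6.c is therefore not quite the test whose 5% level is quoted in 6.e. The discrepancy always runs in one direction: standard errors are too small and tests reject slightly too often. Because 6.c and 6.d reuse the method for every outcome, the error repeats across them. Section 6.b also sets no cap on the number of covariates, and for some contrasts each covariate adds to the bias.

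**Working it through.** **Inputs.** 40 per arm and 80 in total, 5% level, effect sizes 0.37 and 0.32 (6.e); 95 enrolled with 15% attrition (Number of Subjects); full ML on all randomized participants (6.b). The documents give no SD or within-person correlation, but the balanced-data results below depend on neither.

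**1. The plan's own power.** Read the effect sizes as Cohen's f, with noncentrality N·f² and F(1, 78).
- Treatment effect: 80 × 0.37² = 10.95, power 90.5% (stated 90%).
- Interaction: 80 × 0.32² = 8.19, power 80.7% (stated 81%).

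Both reproduce, using 78 error degrees of freedom.

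**2. Pre-post interaction under ML, complete data.** The interaction is the between-arm difference in mean change. Two parameters are fitted to the N change scores, so ML uses SS/N where REML uses SS/(N − 2).
- SE ratio = √((N − 2)/N). N = 80: √(78/80) = 0.987, or 1.3% too small. N = 95: √(93/95) = 0.989, or 1.1% too small.
- The likelihood-ratio test rejects when N·ln(1 + F/df) > 3.841, that is, when F > df·(exp(3.841/N) − 1).
- N = 80: the cut-off is 78 × 0.0492 = 3.84, against 3.96 for the exact F test; actual level 5.4%.
- N = 95: the cut-off is 93 × 0.0413 = 3.84, against 3.94; actual level 5.3%.
- REML with a t reference gives 5.0%.

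**3. Dropout.** Random-intercept simulation under the null hypothesis, 95 randomized, 15% missing the second visit at random, 8,000 runs (Monte Carlo SE about 0.24 points). The likelihood-ratio level was 5.1% with within-person correlation 0.5 and 5.6% with 0.7. The ML/REML SE ratio was 0.988 in both. This agrees with step 2.

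**4. Covariates and the interaction.** A baseline covariate entered as a main effect cancels out of each participant's change when data are balanced, so it uses none of the degrees of freedom for this contrast. Simulation with five such covariates (95 randomized, 15% dropout, correlation 0.5) gave a level of 5.0% and an SE ratio of 0.987, so there was no added inflation.

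**5. Covariates and a between-subject treatment effect.** Here covariates do use the relevant degrees of freedom. With five (an assumed number, since the plan sets none), seven parameters are fitted between subjects: intercept, treatment and five covariates.
- N = 80: df = 73, cut-off 73 × 0.0492 = 3.59, level 6.2%.
- N = 95: df = 88, cut-off 88 × 0.0413 = 3.63, level 6.0%.

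**6. Effect on power.** Applying the ML cut-off of 3.84 in place of 3.96 to the interaction at N = 80 gives 81.6%, against 80.7% by the F test.

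**The case against.** The strongest defence is that full ML is what the plan's procedure requires. The models compared in 6.c differ in fixed effects, so their likelihoods and AIC values can be compared under ML but not under REML. That is right, and ML should stay for those comparisons. It does not follow that ML should also supply the final estimate and its standard error.

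The second defence is size. An excess of 0.3 to 0.4 percentage points on the main contrast is unlikely to change any conclusion. That stands too, and it limits this point to a minor improvement.

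A reader might infer more than the documents support:
- *Planned GFI confidence intervals are too narrow.* Section 6 specifies no interval. What holds is that an interval built from the ML fit would be slightly narrow.
- *The level is 5.7% or 5.8%.* Those figures need a normal reference for a Wald test or, for T3 versus T1, an unstructured covariance as well. The plan names neither. At N = 80 a normal reference gives 5.4% even under REML, so much of that excess is not due to ML.
- *With four to six covariates the interaction test runs at 6.0% to 6.7%.* That needs covariate-by-time terms, and the upper end also needs a normal reference. The plan describes covariates but no such interactions.
- *The power statement is invalid.* It reproduces, and it barely moves under ML.

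A separate gap is that 6.c gives no threshold for a difference in fit. If a lower AIC alone decided a one-parameter treatment term, the false-positive rate would be about 16%. That is a larger matter than the choice of estimator and needs its own answer.

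**Conclusion.** The point holds as a small, one-directional inaccuracy. The interaction result is exact for complete, balanced, normally distributed pre-post data, and simulation supports it with a random intercept and dropout at random. The range from 80 to 95 participants covers completers only up to everyone enrolled. The between-subject figure applies to the treatment effect that 6.e also powers; it rests on the assumed five covariates and would be smaller with fewer. Nothing here undermines the sample size or the use of ML for model building. The case for acting is that the correction is nearly free and brings the reported test into line with the 5% F test in 6.e.

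**What to change.** Add one sentence to 6.b. ML is used for the AIC and nested-model comparisons. The chosen model is then refitted by REML, and the BWL-DRL difference in GFI change from baseline, its 95% confidence interval and its two-sided 5% test are taken from that fit with Kenward-Roger degrees of freedom. State that the same applies to the T1-T3 model and to all secondary outcomes. REML likelihoods should not be used to compare models with different fixed effects.

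The cost is that sentence and a software option. Intervals become slightly wider: on the main contrast the standard error rises by about 1.1% to 1.3%, and the t reference adds a little more. No change to sample size, visits or data collection is needed.
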